15.0 RESEARCH PARTICIPANT REGISTRATION AND RANDOMIZATION PROCEDURES

15.1 Subject Registration (at Memorial Sloan-Kettering Cancer Center)

The following person(s) can obtain informed consent: MSKCC: [name]., [name]., [name]., Ph.D., [name]., [name]., [name]., [name]., [name]., [name]., Ph.D., and [name].

Confirm with electronic medical record that the patient has received the Notice of Privacy Practice. This must be obtained before the eligibility confirmation and obtaining of the research informed consent.

Confirm eligibility as defined in the section entitled Criteria for Patient/Subject Eligibility.

Obtain written informed consent, by following procedures defined in section entitled Informed Consent Procedures.

All patients must be registered through the Protocol Patient Registration (PPR) at Memorial Sloan-Kettering Cancer Center. PPR is available Monday through Friday from 8:30am - 5:30pm at [contact], [contact]. The completed signature page of the informed consent form, the completed signature page of the Research Authorization and a completed Eligibility Checklist must be faxed to PPR at the time of registration.

For Participating Centers:

The following person(s) can obtain informed consent:

M.D. Anderson Cancer center: [name]., New York University Medical Center:: [name].; Hackensack University Medical Center: [name]., Roswell Park Cancer Institute: [name].

Central registration for this study will take place at Memorial Sloan Kettering Cancer Center. To complete registration and enroll a patient from an outside center, the study coordinator will fax to Clinical Trials Office at MSKCC the completed MSKCC eligibility checklist, the last page of the signed informed consent, the signature page of the Research Authorization, and supporting source documentation for eligibility questions. If the patient meets all criteria, the patient will be enrolled and then the patient will be assigned a MSKCC study number. The MSKCC registrar will fax back an enrollment confirmation. Patients from all sites must be registered with the Protocol Patient Registration (PPR) at MSKCC before starting therapy, [contact]-

**Memorial Sloan-Kettering Cancer Center
IRB Protocol**

IRB#: 05-098 A(6)

8000, [contact], Hours of operation 8:30 am to 5:30 pm (Eastern Time) Monday through Friday.

During the registration process registering individuals will be required to answer specific eligibility questions and provide the following information:

Registering Individual	[Last, First Name]
Notice of Privacy Status	[Yes, No, N/A]
Research Authorization	[Date]
MSKCC IRB Protocol#	
Attending of Record (if applicable)	[Last, First Name]
Consenting Professional	[Last, First Name]
Informed Consent Date	
Patient's Full Name	[Last, First Name]
Patient MRN	

15.2 Protocol Patient Number

Once eligibility has been established, the patient is assigned an MSKCC Clinical Research Database (CRDB) patient number. This number is unique to the patient and must be written on all data and correspondence for the patient.

15.3 Randomization

NA

16.0 DATA MANAGEMENT ISSUES

A Research Study Assistant (RSA) will be assigned to the study. The responsibilities of the RSA include project compliance, data collection, abstraction and entry, data reporting, regulatory monitoring, problem resolution and prioritization, and coordinate the activities of the protocol study team.

The data collected for this study will be entered into a secured database (Clinical Research Database, CRDB) at Memorial Sloan-Kettering Cancer Center.

Standardized Case Report Forms (CRFs) have been generated for this study. Affiliate sites will be responsible for filling out these MSKCC case report forms. Blank case report forms will be sent to the data managers at each site (for photocopying and use). These forms and the

Memorial Sloan-Kettering Cancer Center IRB Protocol

IRB#: 05-098 A(6)

required source documentation must be submitted to MSKCC in a timely fashion (please see Appendix 4 for schedule of data collection forms). When a patient goes off-study all CRFs are required to be sent to MSKCC no later than 4 weeks after the off-study date. Participating sites must fax case report forms bimonthly to: [contact] to the attention of the RSA. Forms can also be mailed to the address below.

Memorial Sloan-Kettering Cancer Center
Clinical Trials Office
[name]
[name]
[name]

16.1 Quality Assurance

Weekly registration reports will be generated to monitor patient accruals and completeness of registration data. Routine data quality reports will be generated to assess missing data and inconsistencies. Accrual rates and extent and accuracy of evaluations and follow-up will be monitored periodically throughout the study period and potential problems will be brought to the attention of the study team for discussion and action

Random-sample data quality and protocol compliance audits will be conducted by the study team, at a minimum of once a year, more frequently if indicated.

16.2 Data and Safety Monitoring

The Data and Safety Monitoring (DSM) Plans at Memorial Sloan-Kettering Cancer Center were approved by the National Cancer Institute in September 2001. The plans address the new policies set forth by the NCI in the document entitled “Policy of the National Cancer Institute for Data and Safety Monitoring of Clinical Trials” which can be found at: <http://cancertrials.nci.nih.gov/researchers/dsm/index.html>. The DSM Plans at MSKCC were established and are monitored by the Office of Clinical Research. The MSKCC Data and Safety Monitoring Plans can be found on the MSKCC Intranet at: <http://mskweb2.mskcc.org/irb/index.htm>

There are several different mechanisms by which clinical trials are monitored for data, safety and quality. There are institutional processes in place for quality assurance (e.g., protocol monitoring, compliance and data verification audits, therapeutic response, and staff education on clinical research QA) and departmental procedures for quality control, plus there are two institutional committees that are responsible for monitoring the activities of our clinical trials programs. The committees: *Data and Safety Monitoring Committee (DSMC)* for Phase I and

**Memorial Sloan-Kettering Cancer Center
IRB Protocol**

IRB#: 05-098 A(6)

II clinical trials, and the *Data and Safety Monitoring Board (DSMB)* for Phase III clinical trials, report to the Center's Research Council and Institutional Review Board.

During the protocol development and review process, each protocol will be assessed for its level of risk and degree of monitoring required. Every type of protocol (e.g., NIH sponsored, in-house sponsored, industrial sponsored, NCI cooperative group, etc.) Will be addressed and the monitoring procedures will be established at the time of protocol activation
Inclusion of Children in Research

This protocol/project does not include children because the number of children is limited and because the majority are already accessed by a nationwide pediatric cancer research network. This statement is based on exclusion 4b of the NIH Policy and Guidelines on the Inclusion of Children as Participants in Research Involving Human Subjects.

17.0 PROTECTION OF HUMAN SUBJECTS

Inclusion of Children in Research

This protocol/project does not include children because the number of children is limited and because the majority are already accessed by a nationwide pediatric cancer research network. This statement is based on exclusion 4b of the NIH Policy and Guidelines on the Inclusion of Children as Participants in Research Involving Human Subjects.

17.1 Privacy

It is the responsibility of the Research Staff to ensure that protocol patients have received the Center's Notice of Privacy Practices. If the subject has not already done so, MSK personnel must try to obtain acknowledgment before the patient participates in this study.

MSKCC's Privacy Office may allow the use and disclosure of protected health information pursuant to a completed and signed Research Authorization form. The use and disclosure of protected health information will be limited to the individuals described in the Research Authorization form. A Research Authorization form must be completed by the Principal Investigator and approved by the IRB and Privacy Board.

17.2 Serious Adverse Event (SAE) Reporting

At Memorial Sloan-Kettering Cancer Center:

Any SAE must be reported to the IRB as soon as possible but no later than 5 calendar days. The IRB requires a Clinical Research Database (CRDB) AE report to be delivered to the Institutional SAE Manager ([name]) containing the following information:

**Memorial Sloan-Kettering Cancer Center
IRB Protocol**

IRB#: 05-098 A(6)

Fields populated from the CRDB:

- Subject's name (generate the report with only initials if it will be sent outside of MSKCC)
- Medical record number
- Disease/histology (if applicable)
- Protocol number and title

Data needing to be entered:

- The date the adverse event occurred
- The adverse event
- Relationship of the adverse event to the treatment (drug, device, or intervention)
- If the AE was expected
- The severity of the AE
- The intervention
- Detailed text that includes the following information:
 - A explanation of how the AE was handled
 - A description of the subject's condition
 - Indication if the subject remains on the study
 - If an amendment will need to be made to the protocol and/or consent form

The PI's signature and the date it was signed are required on the completed report.

All serious adverse events regardless of severity or relationship must be reported to Ortho Biotech Products, L.P. within 24 hours of the investigational staff's knowledge.

SAE [contact]

***Serious Adverse Event (SAE):**

Any untoward medical occurrence that at any dose:

- results in death,
- is life-threatening (The patient was at risk of death at the time of the event. It does not refer to an event which hypothetically might have caused death if it were more severe.),
- requires inpatient hospitalization or prolongation of existing hospitalization,

Hospitalizations that do not meet these criteria are:

- reasons described in the protocol, e.g., drug administration, protocol-required testing
- social reason in the absence of an AE
- surgery or procedure planned prior to entry into the trial
- results in persistent or significant disability/incapacity,
or
- is a congenital anomaly/birth defect.

Note: Medical and scientific judgment should be exercised in deciding whether expedited reporting is appropriate in other situations, such as important medical events that may not be

**Memorial Sloan-Kettering Cancer Center
IRB Protocol**

IRB#: 05-098 A(6)

immediately life-threatening or result in death or hospitalization but may jeopardize the patient or may require intervention to prevent one of the outcomes listed in the definition above.

18.0 INFORMED CONSENT PROCEDURES

All Patients will be required to sign a statement of informed consent that has been approved by both the sponsor and by the local Institutional Review Board. The principal investigator is responsible for verifying compliance with all aspects of both the protocol and the informed consent process, which must indicate that the patient has received adequate information to make such informed consent.

Patients willing to enroll will be required to sign three copies of the consent form; one will be returned to the patient, one will be filed in the patient's chart, and one copy will be filed with Protocol Patient Registration (PPR) at the Office of Clinical Research.

18.1 Research Authorization

Procedures for obtaining Research Authorization: Before any protocol-specific procedures are carried out, investigators and/or designated staff will fully explain the details of the protocol, study procedures, and the aspects of patient privacy concerning research specific information. In addition to signing the IRB Informed Consent, all patients must sign the Research Authorization component of the informed consent form. The Research Authorization requires a separate set of signatures from the patient. The original signed documents will become part of the patient's medical record, and each patient will receive a copy of the signed documents.

**Memorial Sloan-Kettering Cancer Center
IRB Protocol**

IRB#: 05-098 A(6)

Appendix 1: Patient Questionnaire

Patient Name _____

Study Site Name: _____

In this questionnaire, you will be asked about your itching and the use of anti-itching medications over the past week. Please complete this questionnaire before seeing your doctor.

(1) Overall, how badly has your skin itched over the past week? Please circle only one number.

0 1 2 3 4 5 6 7 8 9 10

No Itching

Itching as
bad as it
can be

(2) Overall, how has your use of prescribed or over the counter medications against itching, e.g., pills, creams, changed in the past week compared to the previous week? Please circle only one item.

- (A) I did not use any medications against itching in the past week
- (B) I used medication against itching in the past week, but the use is less than the previous week
- (C) I used medication against itching in the past week, but there is no change in the use
- (D) I used medication against itching in the past week, but the use is more than the previous week

Patient Signature: _____

Month _____ Day _____ Year _____

Study staff: This questionnaire must be completed, signed and dated by the patient before the patient is seen by the treating physician.

**Memorial Sloan-Kettering Cancer Center
IRB Protocol**

IRB#: 05-098 A(6)

**Appendix 2: Grading Scales for Composite Assessment (CA)
of Index Lesion Disease Severity**

Page 1 of 2

SCALING	0 - No evidence of scaling on the lesion 1* 2 - Mild: Mainly fine scales; lesion partially covered 3* 4 - Moderate: Somewhat coarser scales; lesion partially covered 5* 6 - Severe: Coarse, thick scales; virtually all of the lesion covered; rough surface 7* 8 - Very severe: Coarse, very thick scales; all of the lesion covered; very rough surface
ERYTHEMA	0 - No evidence of erythema, possible brown hyperpigmentation 1* 2 - Mild: Light red lesion 3* 4 - Moderate: Red lesion 5* 6 - Severe: Very red lesion 7* 8 - Very severe: Extremely red lesion
PLAQUE/TUMOR ELEVATION	0 - 0 mm: No evidence of plaque above normal skin level 1 - ≥ 0 to < 0.5 mm: Minimal but definite plaque elevation above normal skin level 2 - ≥ 0.5 to < 1 mm: Slight but definite plaque elevation 3 - ≥ 1 to < 1.5 mm: Mild elevation 4 - ≥ 1.5 to < 2 mm: Moderate elevation 5 - ≥ 2 to < 2.5 mm: Moderate to marked elevation 6 - ≥ 2.5 to < 3 mm: Marked elevation 7 - ≥ 3 to < 3.5 mm: Very marked elevation 8 - ≥ 3.5 mm: Extreme elevation

* For scaling and erythema, intermediate intervals 1, 3, 5 and 7 were to serve as mid-points between the defined grades 0, 2, 4, 6 and 8.

**Memorial Sloan-Kettering Cancer Center
IRB Protocol**

IRB#: 05-098 A(6)

Table Grading Scales for Composite Assessment (CA)
of Index Lesion Disease Severity (continued)

Page 2 of 2

HYPO-/HYPER-PIGMENTATION	
To have been used only when hypopigmentation or hyperpigmentation was the clinical manifestation of CTCL.
 
0 - No evidence of pigmentation change.
 
1*
 
2 - Mild: 25% lighter pigmentation or noticeably darker pigmentation compared to the patient's normal skin pigmentation.
 
3*
 
4 - Moderate: 50% lighter pigmentation or twice as dark pigmentation compared to the patient's normal skin pigmentation.
 
5*
 
6 - Severe: 75% lighter pigmentation or three times as dark pigmentation compared to the patient's normal skin pigmentation.
 
7*
 
8 - Very severe: Nearly complete absence of pigmentation or nearly as dark a pigmentation as could be observed compared to the patient's normal skin pigmentation.

--------------------------	---

* Intermediate intervals 1,3,5 and 7 are to serve as mid-points between the defined grades 0, 2, 4, 6 and 8.

INDEX LESION AREA	
0 - 0 cm² (no measurable area)
 
1 - > 0 and ≤ 4 cm²
 
2 - > 4 and ≤ 10 cm²
 
3 - >10 and ≤ 16 cm²
 
4 - >16 and ≤ 25 cm²
 
5 - >25 and ≤ 35 cm²
 
6 - >35 and ≤ 45 cm²
 
7 - >45 and ≤ 55 cm²
 
8 - > 55 and ≤ 70 cm²
 
9 - >70 and ≤ 90 cm²
 
10 - >90 and ≤ 110 cm²
 
11 - >110 and ≤ 130 cm²
 
12 - >130 and ≤ 155 cm²
 
13 - >155 and ≤ 180 cm²
 
14 - >180 and ≤ 210 cm²
 
15 - >210 and ≤ 240 cm²
 
16 - >240 and ≤ 270 cm²
 
17 - >270 and ≤ 300 cm²
 
18 - >300 cm²

-------------------	--

**Memorial Sloan-Kettering Cancer Center
IRB Protocol**

IRB#: 05-098 A(6)

Appendix 3: Schedule of Protocol Events																
Week	PreRx	W .2	W .4	W .6	W .8	W .10	W .12	W .14	W .14-16	W .14-16	W .16-18	W .18-20	W .22-24	W .26-28	W .30-32	
	Rx Dose 1	Dose 2	Dose 3	Dose 4	Dose 5	Dose 6	Dose 7	Dose 8		Rx Day 1	Rx W .2	Rx W .4	Rx W .8	Rx W .12	Rx W .16	
Resp. Eval.									X						X	
Rx	Do xil	Do xil	Do xil	Do xil	Do xil	Do xil	Do xil	Do xil		Targ retin	Targ retin	Targ retin	Targ retin	Targ retin	Targ retin	
Hx/Px	X	X	X	X	X	X	X	X	X	X	X	X	X	X	X	
KPS	X	X	X	X	X	X	X	X	X	X	X	X	X	X	X	
Toxicity assess.		X	X	X	X	X	X	X	X	X	X	X	X	X	X	
Tumor measurements	X								X***						X***	
Skin score																
Pruritus questionnaire	X								X						X	
CBC	X	X	X	X	X	X	X	X	X	X	X	X	X	X	X	
Fasting: Trigl.*** Cholest.	X								X		X	X	X	X	X	
Lytes, BUN, Cr., AST, ALT, alk. phos., bili., TP, alb., Ca, amylase, UA, gluc	X								X		X	X	X	X	X	
Urinal.	X															
T4, TSH	X								X		X	X	X	X	X	
Echo/MUGA	X															
CT c/a/p*	X								X						X	
Sézary cell CT/Flow	**** X								X						X	
beta-HCG**	X								X							
*Pts. with stage IV (TNM)																
**premenopausal women within 7 days																
***biopsy of residual lesions if CCR																
****fasting triglyc. obtained at each MD visit																
*****Pts. with Sézary syndrome																

Schedule of Protocol Events

**Memorial Sloan-Kettering Cancer Center
IRB Protocol**

IRB#: 05-098 A(6)

Appendix 4

DATA COLLECTION FORM SCHEDULE

FORM	BASELINE	CYCLE	OFFSTUDY	WHEN APPLICABLE
Demographic, Disease & Prior Treatment Form	X			
Comorbidity Form	X			
Original Pathology Reports*	X			
Original Radiology Reports	X			
Treatment & Treatment Modification Form		X	X	
Physical Exam Form		X	X	
Laboratory Form	X			
Toxicity Form		X	X	
Concomitant Drug Form	X	X	X	
Hospitalization Form				X
Patient Status & Outcome Form				X

* Pathology report must be faxed to the MSKCC Clinical Trials Office [contact] at the same time as patient registration that confirms patient has Cutaneous T-Cell Lymphoma.

Schedule:

Baseline: Forms to be submitted within two weeks of registration.

Cycle: To be completed after each cycle and submitted every 4 weeks.

Off-study: To be submitted within four weeks of the protocol completion.

Please submit forms to:

**[name], Research Study Assistant
Memorial Sloan-Kettering Cancer Center
[name]
[name]
[contact]**

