6.0 CRITERIA FOR SUBJECT ELIGIBILITY

6.1 Subject Inclusion Criteria

- Patient \geq 18 years of age.
- Cutaneous T-cell lymphoma: TNM stages IB, IIA, IIB-IV with biopsy documentation within six weeks before treatment. Repeat biopsies are not required within six weeks before treatment for patients with Sézary syndrome and objective evidence of circulating cells.
- KPS \geq 60
- Acceptable organ function: absolute neutrophil count \geq 1500/ μ L, platelet count \geq 100,000/ μ L, bilirubin \leq 1.5x upper limit of normal, creatinine \leq 1.5x upper limit of normal, SGOT (AST) and SGPT (ALT) \leq 2.5x upper limit of normal
- MUGA or 2-d echocardiogram indicating an ejection fraction of \geq 50% within 42 days prior to first dose of study drug. The method used at baseline must be used for later monitoring.
- Patients previously treated with doxorubicin or epirubicin are eligible if the total cumulative dose does not exceed 300 mg/m² for doxorubicin or 540 mg/m² for epirubicin.
- Negative pregnancy test. Effective birth control measures.
- Topical corticosteroids, with the exception of those with high potency (class 1), will be allowed for patients with erythroderma-Sézary syndrome (T4) and tumor stage (T3) with intense pruritus. Therapy with non-prescription emollients will also be allowed on study.

**Memorial Sloan-Kettering Cancer Center
IRB Protocol**

IRB#: 05-098 A(6)

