9.0 TREATMENT/INTERVENTION PLAN

Dosing/Regimen:

Doxil@Dose: 20mg/m² intravenously. Frequency: 2 weeks. Number of Cycles: 8 (16 weeks)

To minimize the risk of infusion-related reactions, the first infusion of DOXIL should be administered over 90 minutes as follows:

10 mL over 1st 10 minutes

**Memorial Sloan-Kettering Cancer Center
IRB Protocol**

IRB#: 05-098 A(6)

20mL over next 10 minutes
 40mL over next 10 minutes
 then, complete the infusion over a total of 90 minutes

Targretin® Dose: 300mg/m² orally Frequency: Daily for at least 16 weeks to be started within 2 weeks of tumor assessment (It is recommended that patients be treated prophylactically with an agent to lower triglycerides such as fenofibrate or atorvastatin)

Schema:

Doxil® every 2 weeks x 8 → response assessment → within 2 weeks of tumor assessment:
 Targretin® x 16 weeks → response assessment, CR/PR → continue Targretin® until relapse.

Dose Modification Guidelines

Patients should be carefully monitored for toxicity. Adverse events, such as palmar-plantar erythrodyesthesia (hand-foot syndrome), hematologic toxicities, and stomatitis may be managed by dose delays and adjustments. Following the first appearance of Grade 1 toxicity, patients will be prescribed topical betamethasone dipropionate (Diprolene) 0.05% gel to use twice daily on hands and feet only until signs and symptoms resolve. Following the first appearance of a Grade 2 or higher adverse event, the dosing should be adjusted or delayed as described in the following tables. Once the dose has been reduced, it should not be increased at a later time.

PALMAR – PLANTAR ERYTHRODYESTHESIA	
Toxicity Grade	Dose Adjustment
1 (mild erythema, swelling, or desquamation not interfering with daily activities)	Redose unless patient has experienced previous Grade 3 or 4 toxicity. If so, delay up to 2 weeks and decrease dose by 25%. Return to original dose interval.
2 (erythema, desquamation, or swelling interfering with, but not precluding normal physical activities; small blisters or ulcerations less than 2 cm in diameter.)	Delay dosing up to 2 weeks or until resolved to Grade 0-1. If after 2 weeks there is no resolution, Doxil® should be discontinued.

**Memorial Sloan-Kettering Cancer Center
IRB Protocol**

IRB#: 05-098 A(6)

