11.0 TOXICITIES/SIDE EFFECTS

Toxicity will be described according to NCI Common Toxicity Criteria (Version 3.0)

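### No toxicity grade is scheduled before the first Doxil dose, so lymphoma signs already on the hands and feet can be counted as Doxil toxicity

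*Combined protocol and SAP*

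**What the plan says.** - **Event schedule (Appendix 3).** The row "Toxicity assess. X X X" starts at week 2. The PreRx column, which also carries Doxil Dose 1, is empty for this row, although history and physical exam, performance status and CBC are marked there.
- **Form schedule (Appendix 4).** "Toxicity Form X X" and "Physical Exam Form X X" are marked under Cycle and Off-study only. "Laboratory Form X" and "Comorbidity Form X" are marked under Baseline.
- **Text (Section 10.1).** Toxicity assessment is listed among the procedures for every two-weekly Doxil visit, with no exception for the first.
- **Grading (Section 11.0).** "Toxicity will be described according to NCI Common Toxicity Criteria (Version 3.0"). Nothing is said about findings already present at entry.
- **Hand-foot table (Section 9.0).** Grade 1 is "mild erythema, swelling, or desquamation not interfering with daily activities". Higher grades add blisters, ulceration and increasing interference with activity.
- **Eligibility (Section 6.1).** Stages IB, IIA and IIB-IV may enter, and tumor-stage (T3) and erythrodermic (T4) patients are named in the topical steroid criterion. Blood limits are set under "Acceptable organ function: absolute neutrophil count" (at least 1500/µL) and platelets (at least 100,000/µL).
- **Skin score (Section 12.7).** SWAT scores patch, plaque and tumor/ulceration in 12 regions, including Hands (5% of body surface) and Feet (7%).

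**The concern.** A toxicity grade recorded only after treatment starts has no within-patient reference. In most diseases the loss is small. Here the disease lies in the skin, and some of its signs are also the signs of the drug's characteristic skin reaction. No eligibility criterion excludes lymphoma on the hands or feet.

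Two things are at stake. The first is the description of toxicity in a single-arm trial of 37, whose rationale (Section 3.0) includes infrequent severe adverse events: any-grade hand-foot rates could include lymphoma that was there before Dose 1. The second is how the Section 9.0 tables are applied, because hand-foot grades are tied to topical treatment, delay, dose reduction and discontinuation.

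**Working it through.** The plan gives no figure for this point, so the check is mainly a comparison of passages.

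**1. Row alignment in Appendix 3.** There are 15 visit columns and 15 cells in the toxicity row. Fourteen are marked, and the only blank is PreRx/Dose 1.

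**2. Text against appendices.** Section 10.1, read literally, covers the Dose 1 visit; Appendix 3 does not. Even on the Section 10.1 reading, Appendix 4 schedules no form to hold a pre-dose grade.

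**3. Overlap of skin signs, and what the baseline skin score captures.**

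| Sign used in the hand-foot table | Scored as lymphoma by SWAT? |
|---|---|
| Erythema | Yes (patch, plaque) |
| Ulceration | Yes (tumor/ulceration) |
| Swelling | Not recorded |
| Desquamation | Not recorded |
| Interference with activity | Not recorded |

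SWAT can show that disease was on the hands or feet, but a hand-foot grade cannot be rebuilt from it. The mouth is not one of its 12 regions, so it gives no baseline for stomatitis.

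**4. Blood counts.** The Section 9.0 table calls ANC 1500-1900 and platelets 75,000-150,000 Grade 1.
- ANC: the whole Grade 1 band is eligible.
- Platelets: (150,000 − 100,000)/(150,000 − 75,000) = 2/3 of the band is eligible.
- Grade 2 begins below 1500 (ANC) and below 75,000 (platelets), and both are ineligible. Only Grade 1 is possible at entry. It carries no dose reduction and can be derived from the baseline laboratory values.

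**5. Can the bias be sized?** Let b be the share of patients with a gradable sign at entry and t the true drug-caused incidence, assumed independent. Suppose every pre-existing sign is counted. Then

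recorded incidence = b + (1 − b)t, and excess patients = 37 × b × (1 − t).

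The documents give neither b nor t. Over an assumed range:
- b = 5%, t = 50%: 37 × 0.05 × 0.50 = 0.9 patients
- b = 20%, t = 30%: 37 × 0.20 × 0.70 = 5.2 patients
- b = 40%, t = 10%: 37 × 0.40 × 0.90 = 13.3 patients

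The result is set by the assumptions, and each value is a ceiling for its b and t because it allows no clinical discrimination. It shows direction only.

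**6. Bearing on the decision rule.** With 24 or more of 37 progression-free, the exact binomial gives a one-sided type I error of 0.0494 at 50% (the 12-month historical median) and power 0.807 at 70%. This agrees with Section 14.0. Toxicity does not enter the rule.

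**The case against.** **The plan does not attribute every graded sign to the drug.** This stands. A reader might infer that lymphoma and baseline abnormalities are recorded as drug toxicity. No section says so, and the content of the Toxicity Form is not shown. The hand-foot table concerns a named adverse event, and its actions follow a first appearance, which suggests something new. What remains is a risk of misattribution.

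**Baseline information exists.** This stands in part. Section 8.0 requires a history, physical exam, dermatologist's skin score and CBC within 14 days before entry. Index lesions are photographed alongside SWAT, and Appendix 2 grades their scaling and erythema. But there are at most four, chosen as representative and not for being on the hands or feet. No baseline Physical Exam Form is listed.

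**Week 2 may not be the first assessment.** On Section 10.1 alone it need not be. That makes the point one of reconciliation, with a missing form behind it.

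**Stronger readings.** One might infer that severe toxicity will be overstated, or that a persistent lymphoma lesion will lead to Doxil being stopped after one dose. The documents support neither as an expected result: no inflation of severe grades is shown, and early stopping would require a misdiagnosis in a patient whose skin was mapped beforehand. Nor does the 12% of body surface on hands and feet (5 + 7) say what share of patients has disease there.

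**The fix leaves the Section 9.0 actions as they are.** True. It supplies the reference grade; how that grade is used is for the clinical team.

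**Conclusion.** The point holds as a gap in data collection and tabulation, mainly for hand and foot signs. The appendices schedule no pre-treatment toxicity grade, Section 10.1 can be read otherwise, and Section 11.0 has no worsening-from-baseline rule. Pre-existing skin signs can therefore be counted as Doxil toxicity and cannot be reliably separated later, so described rates can be biased upward. A grade not taken before Dose 1 cannot be recovered.

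The size is unknown. It depends on how many patients enter with hand or foot disease and on how well clinicians tell the two apart, and the documents give neither. The blood-count part is minor. Safety is not an endpoint in Section 14.0, so the 24-of-37 rule is not directly affected. This is a cheap improvement, not a flaw in the primary analysis.

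**What to change.** 1. In Appendix 3, mark the toxicity assessment in the PreRx column, consistent with Section 10.1.
2. In Appendix 4, mark the Toxicity Form under Baseline, with hands, feet and mouth graded.
3. In Section 11.0, add that toxicity is tabulated as grades new or higher than the pre-treatment grade, with the worst absolute grade beside it.
4. The clinical team must reconcile how signs present before Dose 1 are read against the Section 9.0 tables. No clinical rule is proposed here.

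The cost is two marks, one sentence, and one extra form taking a few minutes per patient at a visit that already includes history, physical exam and CBC. No efficacy rule or sample size changes.
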